### **6.4 Pregnancy**

If, following initiation of the study drug, it is subsequently discovered that a study subject is pregnant or may have been pregnant at the time of study exposure, including during at least 5 half lives after product administration, the investigator must immediately notify the BMS Medical Monitor/designee of this event and complete and forward a Pregnancy Surveillance Form to BMS Designee within 24 hours of awareness of the event and in accordance with SAE reporting procedures described in [Section 6.1.1](#).

In most cases, the study drug will be permanently discontinued in an appropriate manner (eg, dose tapering if necessary for subject safety).

In the rare event that the benefit of continuing study drug is thought to outweigh the risk, after consultation with BMS, the pregnant subject may continue study drug after a thorough discussion of benefits and risk with the subject

Protocol-required procedures for study discontinuation and follow-up must be performed on the subject unless contraindicated by pregnancy (eg, x-ray studies). Other appropriate pregnancy follow-up procedures should be considered if indicated.

The investigator must immediately notify the BMS (or designee) Medical Monitor of this event and complete and forward a Pregnancy Surveillance Form to BMS (or designee) within 24 hours of awareness of the event and in accordance with SAE reporting procedures described in [Section 6.1.1](#).

Follow-up information regarding the course of the pregnancy, including perinatal and neonatal outcome and, where applicable, offspring information must be reported on the Pregnancy Surveillance Form.

Any pregnancy that occurs in a female partner of a male study participant should be reported to BMS. Information on this pregnancy will be collected on the Pregnancy Surveillance Form.

## **6.5 Overdose**

An overdose is defined as the accidental or intentional administration of any dose of a product that is considered both excessive and medically important. All occurrences of overdose must be reported as an SAE (see [Section 6.1.1](#) for reporting details.).

## **6.6 Potential Drug Induced Liver Injury (DILI)**

Wherever possible, timely confirmation of initial liver-related laboratory abnormalities should occur prior to the reporting of a potential DILI event. All occurrences of potential DILIs, meeting the defined criteria, must be reported as SAEs (see [Section 6.1.1](#) for reporting details).

Potential drug induced liver injury is defined as:

- AT (ALT or AST) elevation > 3 times ULN  
AND
- Total bilirubin > 2 times ULN, without initial findings of cholestasis (elevated serum alkaline phosphatase),  
AND
- No other immediately apparent possible causes of AT elevation and hyperbilirubinemia, including, but not limited to, viral hepatitis, pre-existing chronic or acute liver disease, or the administration of other drug(s) known to be hepatotoxic.

## **6.7 Other Safety Considerations**

Any significant worsening noted during interim or final physical examinations, electrocardiogram, x-ray filming, any other potential safety assessment required or not required by protocol should also be recorded as a nonserious or serious AE, as appropriate, and reported accordingly.

## **7 DATA MONITORING COMMITTEE AND OTHER EXTERNAL COMMITTEES**

A Data Monitoring Committee (DMC) will be established to provide oversight of safety and efficacy considerations in protocol CA209238. Additionally, the DMC will provide advice to the sponsor regarding actions the committee deems necessary for the continuing protection of subjects enrolled in the study. The DMC will be charged with assessing such actions in light of an acceptable benefit/risk profile for nivolumab and ipilimumab. The DMC will act in an advisory capacity to BMS and will monitor subject safety and evaluate the available efficacy data for the study. The oncology therapeutic area of BMS has primary responsibility for design and conduct of the study.

When required, adjudicated events will be submitted to the DMC and Health Authorities for review on a specified timeframe in accordance with the adjudication documentation.

The final DMC meeting occurred on 28-Apr-2020.

## **8 STATISTICAL CONSIDERATIONS**

As of Revised Protocol 06, all planned analyses were conducted based on the 48-month minimum follow-up database lock, which occurred in Jan-2020. No additional formal efficacy analyses will be conducted for newly collected efficacy data. Exploratory analysis on these new efficacy data will be conducted using similar analyses described in the Clinical Study Report (CSR) Statistical Analysis Plan (SAP) for the 48-month minimum follow-up database lock. Exploratory analyses will be performed, eg, every other year, though the analysis schedule might be adjusted based on the additional number of events accumulated.

### **8.1 Sample Size Determination**

The sample size is calculated to compare RFS between subjects randomized to receive nivolumab vs ipilimumab. RFS will be evaluated for a treatment effect at an overall alpha level of 0.05 (two-sided) with approximately 85% power. The number of events and power were calculated assuming a delayed treatment effect and cure fraction.

Approximately 900 subjects have been randomized to the two treatment arms in a 1:1 ratio. Based on current accrual and revised piece-wise accrual rate assumptions, accrual duration was 7.5 months. Taking into account the actual AJCC disease stage distribution, slower event rate, higher cure rates, and some early drop-out, the original planned 507 events might not be reached by the final RFS analysis (ie, after all subjects have a minimum of 36 months of follow-up). Approximately 450 RFS events are anticipated at the final RFS analysis, ensuring at least 85% power to detect a hazard ratio of 0.75 (critical hazard ratio of 0.83) with an overall type I error of 0.05 (two-sided). Sample size calculations for this study design were done using EAST 6 (v 6.3.1) and R.

An interim analysis of RFS will take place after all subjects have a minimum of 18 months of follow-up. Approximately 350 RFS events are anticipated at this analysis. The stopping boundary at the interim analysis will be derived based on the exact number of RFS events at interim using Lan-DeMets alpha spending function with O'Brien-Fleming boundaries. With an interim RFS analysis at 350 RFS events (about 78% information fraction), the critical hazard ratio would be 0.78 and the type I error would be 0.022 (two-sided). The type I error to be used for final RFS analysis would be 0.043 (two-sided).

### **8.2 Populations for Analyses**

- All enrolled subjects: All subjects who signed an informed consent form and were registered into the IVRS.
- All randomized subjects: All subjects who were randomized to any treatment arm in the study.
- All treated subjects: All subjects who received any study drug nivolumab or ipilimumab including placebo doses.

• [REDACTED]  
[REDACTED]  
[REDACTED]

### 8.3 Endpoints

#### 8.3.1 *Primary Endpoint(s)*

The primary endpoint is RFS. The primary endpoint of RFS will be programmatically determined based on the disease recurrence date provided by the investigator and is defined as the time between the date of randomization and the date of first recurrence (local, regional or distant metastasis), new primary melanoma, or death (whatever the cause), whichever occurs first. (Note: a subject who dies without reported recurrence will be considered to have recurred on the date of death.) For subjects who remain alive and whose disease has not recurred, RFS will be censored on the date of last evaluable disease assessment. For those subjects who remained alive and had no recorded post-randomization tumor assessment, RFS will be censored on the day of randomization. Censoring rules for the primary analysis of RFS are presented in [Table 8.3.1-1](#).

**Table 8.3.1-1: Censoring Scheme for Primary Definition of RFS**

Situation	Date of Event or Censoring	Outcome
Recurrence (local, regional, distant, new primary melanoma)	Date of first recurrence	Event
Death without recurrence	Date of death	Event
Disease at baseline	Date of randomization	Event
No baseline disease assessment	Date of randomization	Censored
No on-study disease assessments and no death	Date of randomization	Censored
No recurrence and no death	Date of last evaluable disease assessment	Censored
New anticancer therapy, tumor-directed radiotherapy, or tumor-directed surgery received without recurrence reported prior to or on the same day of disease assessment	Date of last evaluable disease assessment prior to or on the same date of initiation of subsequent therapy	Censored
Second non-melanoma primary cancer reported prior or on the same day of disease assessment	Date of last evaluable disease assessment prior to or on the same date of diagnosis of second non-melanoma primary cancer	Censored

RFS, recurrence-free survival

As of Revised Protocol 06, since no study-specified surveillance assessments are to be collected beyond Year 5, the censoring rules for defining RFS will be different from the primary definition above. RFS will be defined as the time between the date of randomization and the date of first recurrence (local, regional, or distant metastasis), new primary melanoma, or death (whatever the cause), whichever occurs first. (Note: A subject who dies without reported recurrence will be considered to have recurred on the date of death.) For subjects who remain alive and whose disease has not recurred, RFS will be censored on the last date the subject was known to be alive. Censoring rules for the exploratory analysis of RFS are presented in Table 8.3.1-2.

**Table 8.3.1-2: Censoring Scheme for Definition of RFS**

Situation	Date of Event or Censoring	Outcome
Recurrence (local, regional, distant, new primary melanoma)	Date of first recurrence	Event
Death without recurrence	Date of death	Event
Disease at baseline	Date of randomization	Event
No baseline disease assessment	Date of randomization	Censored
No on-study disease assessments and no death	Date of randomization	Censored
No recurrence and no death	Date last known to be alive	Censored
New anticancer therapy, tumor-directed radiotherapy, or tumor-directed surgery received	Date of initiation of subsequent therapy	Censored

**Table 8.3.1-2: Censoring Scheme for Definition of RFS**

Situation	Date of Event or Censoring	Outcome
without recurrence reported prior to or on the same day of disease assessment		
Second non-melanoma primary cancer reported prior or on the same day of disease assessment	Date of diagnosis of second non-melanoma primary cancer	Censored

RFS, recurrence-free survival

**8.3.2 Secondary Endpoint(s)**

The first secondary endpoint (OS) is defined as the time between the date of randomization and the date of death. For subjects without documentation of death, OS will be censored on the last date the subject was known to be alive. OS will be followed continuously while subjects are on the study drug and every 3 months via in-person or phone contact after subjects discontinue the study drug.

The second secondary endpoint (to assess the safety and tolerability of nivolumab and ipilimumab) will be measured by the incidence of adverse events, serious adverse events, deaths, and laboratory abnormalities.

The third secondary endpoint (to evaluate PD-L1 expression as a predictive biomarker) will be measured by the endpoint RFS based on PD-L1 expression level.

The fourth secondary objective (to evaluate HRQoL) will be measured by mean changes from baseline in the EORTC-QLQ-C30 global health status/QoL composite scale and by mean changes from baseline in the remaining EORTC QLQ-C30 scales in all randomized subjects.

[REDACTED]

[REDACTED]

[REDACTED]

[REDACTED]

[REDACTED]

[REDACTED]

[REDACTED]

[REDACTED]

[REDACTED]

## **8.4 Analyses**

### **8.4.1 Demographics and Baseline Characteristics**

Demographic and baseline characteristics will be summarized by treatment arm as randomized using descriptive statistics for all randomized subjects.

### **8.4.2 Efficacy Analyses**

#### **8.4.2.1 Primary Endpoint Methods**

The primary RFS analyses will be conducted using a two-sided log-rank test stratified by PD-L1 status and Stage at screening in randomized subjects. The hazard ratio and corresponding two-sided (1-adjusted  $\alpha$ )% CI will be estimated using a Cox proportional hazards model, with treatment group as a single covariate, stratified by the above factors. RFS curves, RFS medians with 95% CIs, and RFS rates at 6, 12, 18, 24 and 36 months with 95% CIs will be estimated using Kaplan-Meier methodology.

#### **8.4.2.2 Secondary Endpoint Methods**

The secondary OS analysis will be conducted using a two-sided log-rank test stratified by PD-L1 status and Stage at screening in randomized subjects. The hazard ratio and corresponding two-sided (1-adjusted  $\alpha$ )% CI will be estimated using a Cox proportional hazards model, with treatment arm as a single covariate, stratified by the above factors. OS curves, OS medians with 95% CIs and OS rates at 12 and 24 months with 95% CIs will be estimated using Kaplan-Meier methodology.

To evaluate PD-L1 expression as a predictive biomarker, a Cox proportional hazards model will be used to test the interaction between PD-L1 expression (positive vs negative) and treatment arm for the RFS endpoint. Additionally, RFS will be analyzed within each PD-L1 expression subgroup (positive and negative) including log-rank tests and hazard ratios with corresponding confidence intervals. RFS curves and medians will be estimated using Kaplan-Meier methodology. These analyses will be descriptive and not adjusted for multiplicity. Other exploratory analyses, such as associations between PD-L1 expression and other efficacy endpoints and evaluations of different thresholds for PD-L1 positivity, will also be planned in the SAP.

### **8.4.3 Safety Analyses**

Safety analyses will be performed in all treated subjects. Descriptive statistics of safety will be presented using NCI CTCAE version 4.0 by treatment group. All on-study AEs, treatment-related AEs, SAEs, and treatment-related SAEs will be tabulated using worst grade per NCI CTCAE v 4.0 criteria by system organ class and preferred term. On-study lab parameters including hematology, chemistry, liver function, and renal function will be summarized using worst grade NCI CTCAE v 4.0 criteria.

[REDACTED]

[REDACTED]

[REDACTED]

#### **8.4.6 Outcomes Research Analyses**

##### **EORTC QLQ C-30**

The analysis of EORTC QLQ C-30 will be performed in all randomized who have an assessment at baseline and at least one follow-up assessment.

All scales and single items are scored on a categorical scales and linearly transformed to 0-to-100 scales with higher scores for a functional scale representing higher levels of functioning, higher scores for the global health status/quality of life representing higher levels of global health status/quality of life and higher scores for a symptom scale representing higher level of symptoms.

EORTC QLQ C-30 global health status/QoL composite scale data and the remaining EORTC QLQ C-30 scale data will be summarized by timepoint using descriptive statistics for each treatment arm. Exploratory analyses may be performed to examine differences between the 2 arms.

[REDACTED]

[REDACTED]

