### 1.3.2 Secondary Objectives

- To compare the overall survival of nivolumab vs ipilimumab in subjects with completely resected Stage IIIb/c or Stage IV NED melanoma who are at high risk for recurrence.
- To assess the overall safety and tolerability of nivolumab and ipilimumab in subjects with completely resected Stage IIIb/c or Stage IV NED melanoma who are at high risk for recurrence.
- To evaluate whether PD-L1 expression is a predictive biomarker for RFS.
- To evaluate the Health Related Quality of Life (HRQoL) as assessed by European Organisation for Research and Treatment of Cancer (EORTC) QLQ-C30.

[REDACTED]

[REDACTED]

[REDACTED]

[REDACTED]

[REDACTED]

[REDACTED]

[REDACTED]

[REDACTED]

[REDACTED]

[REDACTED]

[REDACTED]

[REDACTED]

[REDACTED]

[REDACTED]

[REDACTED]

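### The only committed HRQoL analysis is descriptive, available-case summaries by visit; with no longitudinal model or missing-data assumption, HRQoL-related discontinuation that differs between arms could distort the arm difference.

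*Protocol*

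**What the plan says.** Protocol section 1.3.2 makes HRQoL a secondary objective: "To evaluate the Health Related Quality of Life (HRQoL) as assessed by European Organisation for Research and Treatment of Cancer (EORTC) QLQ-C30".

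Section 8.3.2 defines the measure as "mean changes from baseline in the EORTC-QLQ-C30 global health status/QoL composite scale" and "mean changes from baseline in the remaining EORTC QLQ-C30 scales in all randomized subjects".

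Section 8.4.6 sets a narrower population: "The analysis of EORTC QLQ C-30 will be performed in all randomized who have an assessment at baseline and at least one follow-up assessment". The method there is that the data "will be summarized by timepoint using descriptive statistics for each treatment arm". On comparing the arms it says only: "Exploratory analyses may be performed to examine differences between the 2 arms". No method is named for that comparison. The visible text gives no longitudinal model, missing-data assumption or sensitivity analysis.

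Tables 5.1-2 to 5.1-6 schedule the QLQ-C30 at Week 1 (before dosing) and at Weeks 5, 7, 11, 17, 25, 37 and 49. Table 5.1-7 adds Follow-up Visits 1 and 2 and marks no QLQ-C30 at the survival visits. Visit 1 is about 30 days after the last dose (or at discontinuation, if that is later than 37 days after it), and Visit 2 is 84 days after Visit 1. Section 3.1 ends the treatment phase at early discontinuation.

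The supplied SAP is written for the DMC and mentions HRQoL only in its list of objectives. Protocol section 8 refers to a separate CSR SAP, which is not among the documents.

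**The concern.** A by-visit summary of available forms describes whoever is still completing forms at that visit. Someone who stops early is in the Week 5 summary but not the Week 37 or Week 49 one. The subjects behind the mean therefore change over time, and they need not change in the same way in both arms.

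The protocol makes a link between stopping and HRQoL plausible. Section 3.5 requires discontinuation for recurrence, for adverse events that the investigator judges important, and at the subject's request. Section 4.5.7 adds a list of drug-related toxicities. Any of these may go with a change in how a subject feels. Different patterns by arm are also plausible: both arms receive an active drug, the drugs differ, and the trial is designed around a difference in recurrence (hazard ratio 0.75, section 8.1).

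At stake is the reading of a quality-of-life comparison between two active treatments. Readers will compare the arms' visit means whether or not a test is planned. RFS and OS are not affected.

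**Working it through.** **1. Who leaves the visit summaries.** Take a subject whose last dose is at Week 11. Follow-up Visit 1 falls 30 days later and Visit 2 a further 84 days later, so the last scheduled form comes 30 + 84 = 114 days, or 114/7 = 16.3 weeks, after the last dose. That is about Week 27. No form is due near Week 37 or Week 49. The two follow-up forms are timed from the last dose, and section 8.4.6 does not say how they enter a summary by timepoint.

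**2. Populations side by side.** Section 8.3.2: all randomized subjects. Section 8.4.6: randomized subjects with a baseline form and at least one later form. These are different sets.

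**3. Does the available-case summary mislead, and when?** The documents give no HRQoL standard deviation, target difference, completion rate or discontinuation rate, so there is no stated figure to reproduce. A simulation shows the mechanism only.

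- From the documents: about 900 subjects randomized 1:1, so 450 per arm; baseline plus the seven on-treatment visits.
- Assumed: SD 20; true Week 49 difference 5 points in favour of arm Y, the arm with fewer discontinuations; correlation either exchangeable 0.6 or AR(1) 0.8; monotone dropout; no forms counted after discontinuation; 400 runs per scenario.
- Estimators at Week 49 (Y minus X): observed raw mean, observed mean change from baseline, and a baseline-adjusted repeated-measures estimate.

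Ranges cover the two correlation structures. MAR means missing at random, MNAR missing not at random.

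| Dropout rule | Discontinued X / Y | Raw mean | Mean change | Model |
|---|---|---|---|---|
| (a) Unrelated to HRQoL | 50% / 30% | 5.0 to 5.1 | 5.1 to 5.2 | 5.1 |
| (b) Last observed decline, X only (MAR) | 59% / 30% | 1.6 to 5.1 | -4.3 to 0.0 | 5.0 |
| (c) Last observed level, X only (MAR) | 59% / 30% | -2.8 to -1.2 | 5.7 to 6.2 | 5.0 |
| (d) Current unobserved level or decline, X only (MNAR) | 60% / 30% | -4.0 to 4.1 | -6.7 to 4.0 | 1.6 to 2.1 |
| (e) Last observed decline, same moderate dependence in both arms (MAR) | 56% / 33-34% | 3.8 to 5.1 | 1.7 to 3.5 | 5.0 to 5.1 |
| (f) Last observed decline, same strong dependence and similar rates (MAR) | 39-40% / 36-37% | 4.9 to 5.0 | 4.4 to 4.7 | 5.0 to 5.1 |

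Four things follow.

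- Unequal rates alone do no harm (a).
- HRQoL-related dropout at similar rates does little (f).
- The two together distort mean change, and the direction depends on the rule: it shrinks or reverses in (b) and (e), and overshoots in (c).
- The model is right under MAR and wrong under MNAR. With a true difference of 2 and dropout driven by the current unobserved decline in X, it gave -1.4 to -0.6, the wrong sign.

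**4. Precision.** With baseline correlation r and equal variances, the variance of a baseline-adjusted comparison relative to a change-score comparison is (1 - r²) / [2(1 - r)] = (1 + r)/2. At r = 0.7 this is 0.85, and at r = 0.4 it is 0.70. That is a 15% to 30% reduction for those assumed correlations.

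**The case against.** The strongest reply is that the governing plan has not been seen. The CSR SAP may contain a longitudinal model, part of section 8.4.6 is redacted, and other parts of protocol section 8 leave detail to a SAP. This stands: the most that can be said is that no such model appears in the supplied text. It is still notable that the PD-L1 objective, also descriptive, gets a named interaction model and a pointer to the SAP in section 8.4.2.2, while the visible HRQoL text has neither.

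Second, no HRQoL test is planned. The objective is to evaluate rather than compare, and HRQoL lies outside the testing hierarchy of section 8.5. This also stands, and it limits the point to estimation. It does not remove it, because descriptive means by arm invite the comparison.

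Third, some data are collected off schedule. Section 4.5.7 keeps questionnaires going through omitted doses, section 5.7 says the instruments go to all randomized subjects, and discontinued subjects have two follow-up forms. This reduces the loss, and the simulation gives no credit for those two forms. It does not put discontinued subjects back into the later on-treatment visits. The follow-up bullets in section 3.1 point to Table 5.1-6 for PRO timing, but that table covers dosing Weeks 41 to 51, whereas section 5.7 also lists the follow-up table.

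Stronger readings are tempting, and the documents do not support them:

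- That raw visit means are the endpoint. Section 8.3.2 specifies change from baseline.
- That different discontinuation rates by themselves bias the result. Row (a) shows that they do not.
- That the bias must favour the arm with more toxicity-driven stopping. Row (c) goes the other way on mean change.
- That a mixed model would recover the true difference. It does so only under MAR, and stopping because one currently feels worse may well be MNAR.

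**Conclusion.** The point holds in a limited form. In the supplied documents, the committed analysis of a secondary objective is available-case description by visit, including mean change from baseline, with no stated missing-data assumption and with two different populations. Such summaries can hide, exaggerate or reverse an arm difference if discontinuation is related to HRQoL and differs between arms.

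Whether that happened here, how much and in which direction cannot be known from the documents. The spread of observed mean change against a true 5 points (-4.3 to 6.2 under MAR, -6.7 to 4.0 under MNAR) rests on the assumed SD, correlations, discontinuation rates and dropout rules. It illustrates the mechanism and is not an estimate for this trial.

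This is a worthwhile, inexpensive improvement. It is not a flaw that threatens the trial's main conclusions, and it may already be met in the CSR SAP.

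**What to change.** In protocol section 8.4.6, or in the SAP that it should cite:

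- Add a mixed model for repeated measures of change from baseline in randomized subjects with a baseline and at least one post-baseline form. Include arm, visit, arm-by-visit, baseline score, PD-L1 status and stage, with unstructured covariance. Report the arm difference with a 95% CI at each visit.
- Alternatively, use a constrained longitudinal model with baseline as an outcome. A model with baseline as a covariate needs a baseline form; the constrained model admits every randomized subject with any form.
- State the MAR assumption and add an MNAR sensitivity analysis. Say how the follow-up forms are used and what the estimate means for subjects who stopped because of recurrence.
- Tabulate form completion by arm and visit, and keep the descriptive tables.
- Reconcile the populations in sections 8.3.2 and 8.4.6.

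Keep this as estimation only, outside the testing hierarchy. Label it supplementary, because section 8 says that the planned analyses used the January 2020 lock. If the CSR SAP already has such a model, cite it instead.

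Cost: a few lines of text, one standard model and a sensitivity analysis on data already collected. The downside is reliance on MAR in the main estimate, which is why the sensitivity analysis belongs with it.
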